## 7.6 Subgroup Analyses

The primary efficacy analysis will be presented by investigator site as well as by key demographic or baseline characteristics, including concurrent anticholinergic therapy (use and nonuse), baseline daytime urinary incontinence episodes (a total of  $\leq$  6 episodes or  $>$  6 episodes over the 2-day diary collection period), age ( $<$  12 years or  $\geq$  12 years), race, and sex.

## 7.7 Sample Size Calculation

The sample size calculation for this study is determined empirically, while taking into account the treatment effect observed in the adult pivotal phase 3 studies, 191622-515 and 191622-516. The mean (standard deviation) of the change from baseline in daily urinary incontinence at week 6 was -3.1 (3.44) and -3.1 (2.58) in Studies 191622-515 and 191622-516, respectively.

Approximately 34 patients per treatment group are to be enrolled for the study. This includes 30 patients per treatment group and an increase to 34 per group in order to address patient attrition (estimated to be 10% by week 6)

The following table displays estimates of the distance for treatment differences between BOTOX 200 U (maximum 6 U/kg) and 50 U (maximum 6 U/kg) in mean daily average frequency of daytime episodes of urinary incontinence change from baseline at week 6 for a range of common standard deviations (SD). All calculations assume 30 patients per treatment group and a 2-sided test significance level of 0.05. The calculation was performed using the commercial software nQuery Advisor (procedure MTC0-1), version 6.01, and the CI is based on the large sample z statistic.

Standard Deviation	Distance From Mean to the Limit
2.0	1.012
2.5	1.265
3.0	1.518
3.5	1.771
4.0	2.024

Note: The ranges of the SDs are determined based on the values from the adult pivotal phase 3 studies (191622-515 and 191622-516). The estimate of the SD for the 200 U BOTOX treatment group is 3.44 for Study 191622-515, 2.58 for Study 191622-516, and 3.10 for the 2 studies combined.

## 7.8 Interim Analyses

No interim analysis is planned for this study.

## 8 Study Visit Schedule and Procedures

Please see [Table 1](#) for a schematic of the schedule of visits and procedures, [Figure 1](#) for the visit flow chart, and Section [6.3](#) for detailed information on study procedures, tests, equipment, and techniques.

### 8.1 Patient Entry Procedures

#### 8.1.1 Overview of Entry Procedures

Prospective patients as defined by the criteria in Sections [4.3](#) and [4.4](#) (Inclusion/Exclusion Criteria) will be considered for entry into this study.

#### 8.1.2 Informed Consent and Patient Privacy

The study will be discussed with the patient/legally authorized representative and a patient wishing to participate or his/her legally authorized representative must give informed consent and, when applicable, minor assent prior to any study-related procedures or change in treatment. The patient/legally authorized representative must also give authorization (US only), data protection consent (Europe only), and other written documentation in accordance with the relevant country and local privacy requirements (where applicable) prior to any study-related activities or procedures.

Further information is provided in Section [10.1](#).

Each patient who provides informed consent and/or assent will be assigned a patient number via IVRS/IWRS that will be used on patient documentation throughout the study.

## 8.2 Procedures for Final Study Entry

Final study eligibility will be determined at [REDACTED] to confirm that patient bladder diary records support protocol requirements for urinary incontinence. In addition, prior to randomization, the investigator should confirm that the day of treatment criteria have been fulfilled (Section 5.9.1). Patients should continue to meet other inclusion and exclusion criteria as specified in Sections 4.3 and 4.4 of the protocol.

A patient is considered to have entered the study when they are randomized to treatment.

See Section 5.5 for the method for assignment to treatment groups/randomization.

## 8.3 Visits and Associated Procedures

For a summary of the procedures to be performed, [REDACTED]

[REDACTED] A description of individual procedures is provided in Section 6.3. The total number of clinic visits and study duration for each patient will depend on whether patients request and qualify for retreatment. Evaluations should be performed by the same evaluator throughout the study whenever possible. [REDACTED]

## 8.4 Instructions for the Patients

Patients/parents/caregivers will be instructed on the following:

- to strictly follow the study visit schedule and report any changes in condition to the investigative site
- to maintain the dose of any concurrent medication and anticholinergic medication during the study whenever possible (except anticholinergic medication which can be modified as described in Section 4.5.1)
- to remain on the same CIC regimen
- to change wet pads/diapers/underwear as soon as possible during diary collection periods in order to accurately capture episodes of incontinence

- to call the study site if they are experiencing any difficulties following study treatment administration or study procedures
- to contact the study site to report any hospitalizations
- to call the study site as soon as possible in order to reschedule, if the patient cannot make their next scheduled study visit
- diaries should be completed and brought to the study site at each scheduled clinic study visit

## **8.5                   Unscheduled Visits**

Unscheduled visits can be performed if safety concerns arise and at the discretion of the investigator. Additional examinations may be performed as necessary to ensure the safety and well being of patients during the study. eCRFs will be completed for each unscheduled visit.

## **8.6                   Compliance with Protocol**

Participating patients (or parents/caregivers) should be able to adhere to the diary completion and testing parameters as described in this protocol.

Data will be recorded on the appropriate eCRF supported by appropriate source documentation. At each visit, patients/parents/caregivers should be asked if any concomitant medications had been used, if they had undergone any concurrent procedures (nonstudy procedures), and their compliance with the protocol since the previous visit.

## **8.7                   Early Discontinuation of Patients**

Patients may voluntarily withdraw from the study at any time. Patient discontinuation from the study and the reason for early discontinuation will be clearly documented on the appropriate eCRF. Patients who agree to follow-up will be followed for a minimum of 12 weeks after study treatment for safety as per the protocol. If a patient exits the study prior to study completion, all assessments for that visit should be performed in addition to any other exit visit assessments.

## 8.8 Withdrawal Criteria

Patients have the right to withdraw from the study at any time and for any reason without prejudice to his or her future medical care by the physician or the institution. The investigator and Allergan also have the right to withdraw a patient from the study at any time for any reason.

Patients should be discontinued from the study if any of the following criteria are met. Where possible, the decision to withdraw a patient from study treatment or the study should be discussed with Allergan.

- patient develops (or has an exacerbation of) any medical condition that, in the opinion of the investigator, would put the patient at an unacceptable medical risk or compromises the patient's ability to participate in the study
- patient becomes pregnant (see Section 4.5.1.1 Definition of Females of Childbearing Potential and Acceptable Contraceptive Methods)
- patient/parent/caregiver is unwilling or unable to continue to comply with study procedures

## 8.9 Study Termination

The study may be stopped at his/her study site at any time by the site investigator. Allergan may stop the study (and/or the study site) for any reason with appropriate notification.

# 9 Adverse Events

Throughout the course of the study, all adverse events will be monitored and reported on an adverse event case report form, including seriousness, severity, action taken, and relationship to study drug or injection procedure. If adverse events occur, the first concern will be the safety of the study participants.

## 9.1 Definitions

### 9.1.1 Adverse Event

Any untoward medical occurrence in a patient or clinical investigation patient administered a pharmaceutical product and that does not necessarily have a causal relationship with this treatment. An adverse event can therefore be any unfavorable and unintended sign (including an abnormal laboratory finding), symptom, or disease temporally associated with the use of a medicinal (investigational) product, whether or not related to the medicinal (investigational)

product. In addition, during the screening period, adverse events will be assessed regardless of the administration of a pharmaceutical product.

Note: Adverse events must be collected once informed consent has been obtained, regardless of whether or not the patient has been administered study drug.

Progression of NDO, including new or worsening of anticipated clinical signs or symptoms, which are collected as clinical efficacy variables and assessed as unequivocally associated with the disease progression and /or lack of efficacy, should not be reported as adverse events unless the disease progression is greater than anticipated in the natural course of the disease.

Adverse events will be assessed, documented, and recorded in the eCRF throughout the study (ie, after informed consent/assent has been obtained). At each visit, the investigator will begin by querying for adverse events by asking each patient or parent/caregiver a general, non-directed question such as “How have you been feeling since the last visit?” Directed questioning and examination will then be done as appropriate. All reported adverse events will be documented on the appropriate eCRF.

### **9.1.2        Definition of Adverse Events of Urinary Tract Infection and Urinary Retention**

Study-specific definitions for the adverse events of UTI and urinary retention are provided below.

#### *Adverse Event of Urinary Tract Infection*

An adverse event of UTI is defined as being a symptomatic UTI that requires treatment in the opinion of the investigator.

#### *Adverse Event of Urinary Retention*

Urinary retention should only be reported in patients who had the ability to spontaneously void between catheterizations prior to study treatment. It is defined in these patients as the inability to spontaneously void for at least 24 hours, which is not in conjunction with the patient experiencing constipation.

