### *Key Inclusion Criteria:*

- patient must be regularly using clean intermittent catheterization (CIC) to empty the bladder

*Key Exclusion Criteria:*

- patient has had surgery of the spinal cord within 6 months of screening

- patient has cerebral palsy

- patient currently uses or plans to use a baclofen pump
- patient currently uses or plans to use an implantable or nonimplantable electrostimulation/neuromodulation device for treatment of NDO. (If a nonimplantable device is used, it must be discontinued at least 7 days prior to the first screening procedure; if a device is implanted, it must be inactive for at least 4 weeks prior to the first screening procedure; neither should be used during the study).
- patient uses an indwelling catheter, rather than CIC, for treatment of NDO (NOTE: an indwelling catheter can be used if needed overnight, as long as it is not used during the diary collection periods)
- patient has had previous or current:
  - botulinum toxin therapy of any serotype for any urological condition, or
  - treatment with botulinum toxin of any serotype within 3 months of randomization/day 1 for any other condition or use

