With respect to safety, adverse events were primarily limited to local adverse events related to the urinary tract, in particular urinary retention and urinary tract infection (UTI). In patients not using CIC prior to treatment, a dose-dependent increase in post-void residual urine volume was observed posttreatment. A proportion of patients, both in the placebo and active dose groups, initiated CIC that was also dose-dependent.

A consistent efficacy and safety profile has been demonstrated with repeat BOTOX treatment. The reductions from baseline in urinary incontinence episodes remained similar

over repeated BOTOX treatments, as did the improvement in HRQOL. The most common adverse events remained urological (eg, urinary tract infection and urinary retention), and the incidence of such adverse events did not increase with repeated BOTOX treatment.

Since there was no additional efficacy or benefit with the 300 U BOTOX dose compared to the 200 U BOTOX dose, and given that the 200 U BOTOX dose displayed a better safety profile, 200 U BOTOX was submitted for licensing registration, and approval has subsequently been granted in many countries at this dose.

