#### 7.4 Safety Analyses

All safety analyses will be conducted on the safety population. Safety variables are adverse events, serious adverse events, [REDACTED]

[REDACTED]  
[REDACTED]  
[REDACTED]

[REDACTED]  
[REDACTED]  
[REDACTED]  
[REDACTED]

[REDACTED]  
[REDACTED]  
[REDACTED]

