The mITT population will include all randomized patients who received BOTOX injection on Day 1 (randomization day and date of injection). Patients in the mITT population will be analyzed on an as-randomized basis, except for patients who received less than their randomized dose due to the patient's weight and the dose limit of 6 U/kg (as per the protocol). Such patients will be grouped to the nearest dose group based on the dose they actually received. Thus, patients that receive a dose of < 75 U will be assigned to the 50 U treatment group, patients that received a dose in the range of ≥ 75 U and < 150 will be assigned to the 100 U treatment group, while patients that received ≥ 150 U will be assigned to the 200 U group ([Table 1](#)). Patients who received a different dose for any other reason than the 6 U/kg cap, will be analyzed according to the dose they were randomized to.

Safety Population

The safety population will include all patients who underwent the treatment procedure and received study drug on randomization/day 1. Safety analyses will be based on actual treatment received. Patients who received a different dose than the dose they were randomized to (as a result of either the 6 U/kg weight cap or any other reason) will be grouped according to the nearest dose group based on the actual dose received, as presented in [Table 1](#).

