6.2 Adverse Events

[figure not shown]
Adverse events (AEs) will be coded by system organ class and preferred term using the Medical Dictionary for Regulatory Activities (MedDRA).

[figure not shown]
Pre-treatment AEs are AEs that have start date on or after the signing of consent form and prior to the BOTOX injection.

[figure not shown]
An AE will be considered a treatment-emergent adverse event (TEAE) if it was present after the first dose of study treatment or was present before the date of the first dose of study treatment and increased in severity or became serious after the first dose of study treatment.

[figure not shown]
The number and percentage of patients reporting TEAE in each treatment group will be tabulated by descending percentage in any group, by system organ class and preferred term, and further categorized by severity and causal relationship to the study drug and study drug injection procedure. If more than 1 AE is coded to the same patient, the patient will be

[figure not shown]
counted only once for that preferred term using the greatest severity for the summarization by severity and causal relationship.

[figure not shown]

[figure not shown]
[figure not shown]

[figure not shown]

9. Interim Analyses

No interim analysis is planned for this study. However, there is a Data Review Committee (DRC) that reviews, on regular bases, selected blinded safety analyses. There is a separate DRC charter and analysis plan that outlines the function of the DRC and what they will be reviewing.

10. Analysis for US FDA

Not applicable.

11. Data Collected but not Analyzed

A patient's surgical history and female patients' birth control treatment during the study are collected in this study. No output will be generated for these data.

12. Deviations from Protocol

There are no deviations from the protocol.

13. References

Mallinckrodt CH, Clark WS, David SR (2001a). Type I error rates from mixed-effects model repeated measures versus fixed effects analysis of variance with missing values imputed via last observation carried forward. *Drug Information J*. 2001a;35:1215-1225.

Mallinckrodt CH, Clark WS, David, S. R. (2001b). Accounting for dropout bias using mixed-effects models. *J. Biopharmaceutical Statistics*. 2001b;11:9-21.

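### Urinary retention can be reported only in children who could void before treatment, but the visible adverse event table divides by every treated child in the dose group

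*Protocol*

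**What the plan says.** Protocol 9.1.2 gives a study-specific definition of urinary retention as an adverse event. It first limits who may have the event: "Urinary retention should only be reported in patients who had the ability to spontaneously void between catheterizations prior to study treatment". It then defines the event: "It is defined in these patients as the inability to spontaneously void for at least 24 hours", excluding episodes that accompany constipation.

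The Key Inclusion Criteria in the Protocol Summary describe the enrolled population: "patient must be regularly using clean intermittent catheterization (CIC) to empty the bladder". No visible criterion requires that a child can also void spontaneously. Much of Protocol 4.3 is redacted.

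On analysis, Protocol 7.4 says: "All safety analyses will be conducted on the safety population". SAP 2.1 defines that population: "The safety population will include all patients who underwent the treatment procedure and received study drug on randomization/day 1". Patients are grouped by the dose actually received, and voiding status plays no part. SAP 6.2 then says: "The number and percentage of patients reporting TEAE in each treatment group will be tabulated by descending percentage in any group". The rows of that table are MedDRA classes and terms. The visible text gives no separate denominator for retention.

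Protocol 5.4 stratifies by age and baseline daytime incontinence episodes only. Voiding ability is not among the baseline characteristics visible in SAP 4.2. The bladder diary does record voluntary voids as an episode type (Protocol 6.3.6, SAP 2.3.1).

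**The concern.** The numerator is restricted to a subset and the denominator is not. A child who could not void before treatment cannot be reported with retention at any dose, yet counts as a child without the event. The restriction in Protocol 9.1.2 has an effect only if some enrolled children are in that position, so the protocol itself anticipates a mixed population.

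Two consequences follow. The percentage in the table is lower than the risk in the only children who can have the event. A difference between doses, or the lack of one, also partly reflects the mix of voiders and non-voiders in each arm. With voiding ability neither stratified nor in the visible baseline summary, a reader of the table could not correct for that mix.

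The event matters because safety across three doses is a study objective, and Protocol section 1 names retention and urinary tract infection as the leading local adverse events in the adult programme.

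**Working it through.** **Inputs.** Group size is 34, from Protocol 7.7: 30/(1 − 0.10) = 33.3, rounded up to 34, and 3 × 34 = 102, which matches Protocol 4.1. Safety groups are formed by actual dose, so they need not be exactly 34. The share able to void, *q*, and the retention risk among those children, *r*, are not in the documents. Both are assumptions and are shown as ranges.

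**Dilution.** The expected printed percentage is *q* × *r*. It understates *r* by a factor of 1/*q*, whatever the group size or the true risk.

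| Share able to void | Factor 1/*q* | Printed if *r* = 10% | Printed if *r* = 20% | Printed if *r* = 30% |
|---|---|---|---|---|
| 100% | 1.0 | 10% | 20% | 30% |
| 75% | 1.3 | 7.5% | 15% | 22.5% |
| 50% | 2 | 5% | 10% | 15% |
| 20% | 5 | 2% | 4% | 6% |
| 10% | 10 | 1% | 2% | 3% |

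**Imbalance between arms.** Treat the number of voiders in each of two arms as independent Binomial(34, *q*), and sum the joint probabilities over all pairs in which the larger count is at least twice the smaller. The result is about 22% at *q* = 20%, 15% at *q* = 25% and 1% at *q* = 50%. As an illustration, take 5 voiders in one arm and 10 in another, both with a true risk of 20%. The expected events are 5 × 0.20 = 1 and 10 × 0.20 = 2. The expected printed rates are 1/34 = 2.9% and 2/34 = 5.9%, although the risk is the same.

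**Reassurance from zero events.** With no events in *n* patients, the exact two-sided 95% upper limit is 1 − 0.025^(1/*n*). This is 10.3% for *n* = 34, 13.2% for 26, 19.5% for 17, 36.9% for 8 and 70.8% for 3. A zero in the all-patient row looks much more informative than the same zero among the children at risk.

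**How the at-risk group is identified.** Suppose the group were defined by a voluntary void in the baseline diary, plus any child for whom an event is reported. The second route admits voiders whom the diary missed only if they have the event. If the diary detects 70% of voiders (assumed) and the true risk is 30%, the rate becomes 0.30/(0.70 + 0.30 × 0.30) = 0.30/0.79 = 38%. Membership must therefore not depend on the outcome.

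**The case against.** The strongest objection is redaction. Protocol 7.4 is largely blacked out, and of the adverse event and other safety sections of the SAP only 6.2 is readable. The SAP amendment log refers to a 6.2.1 and a 6.4 that cannot be seen. A retention table by voiding status could sit there. This stands: a reader might infer that the plan contains no at-risk analysis, and the documents do not support that.

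The size is also open. A reader might infer that the printed rate will be far below the real risk. That holds only if few children can void. At 75% the factor is 1.3, and if all can void there is no dilution.

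Large contrasts between arms should not be taken as typical. At a 20% share the central 95% range of voiders in an arm of 34 runs from 3 to 12. With a 30% risk those ends give expected rates of 3 × 0.3/34 = 2.6% and 12 × 0.3/34 = 10.6%. The probability that one of two given arms has 3 or fewer and the other 12 or more is only about 0.4%.

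The all-patient percentage is also not an error in itself. It is the crude incidence among treated CIC users on the declared safety population, and the visible SAP 6.2 plans no test between doses. The adult findings do not transfer directly either, since the adult residual-urine finding concerned patients not using CIC and every child here uses it. These points limit the weight of the concern. They do not answer the mismatch, because the crude rate cannot be read as the risk in children able to void, and the visible table gives no means of recovering that risk.

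**Conclusion.** The point holds for the adverse event table as visible in SAP 6.2. Its retention percentage includes children who by definition cannot be reported with the event, and so understates the risk among children able to void by 1/(share able to void). Over assumed shares of 75% down to 10%, the factor is 1.3 to 10. Dose comparisons partly reflect chance differences in the number of voiders: at least twofold about 22% of the time at an assumed 20% share, and about 1% at 50%.

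This rests on reading a percentage per treatment group as one over all safety patients in that group, which is the plain reading although the denominator is not spelled out. It also rests on some enrolled children being unable to void. The primary efficacy result is unaffected, and the event definition in Protocol 9.1.2 is not in dispute. Because the correction is cheap and the event is a named safety concern, it should be made.

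**What to change.** In SAP 6.2:

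- Keep the all-patient retention row, with a footnote that patients without spontaneous voiding before treatment cannot contribute an event.
- Add a row giving retention as n/N, with an exact 95% confidence interval, among safety patients with at least one voluntary void in the baseline diary. Show the at-risk N for each dose group.
- Define that subset from baseline diary data alone, identically for patients with and without events, and fix the rule before unblinding.
- List separately any retention event in a patient outside the subset.
- If a hidden section already contains such an analysis, a cross-reference from 6.2 is enough.

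The cost is SAP wording and one extra row from data already collected. The drawbacks are small denominators, wide intervals, and a 2-day diary that may miss an occasional voider. The separate listing makes visible any events lost in that way.
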